#### 5.1.2 Blood samples

Blood samples will be collected and processed according to validated standard operating procedures (SOPs) to maintain sample quality and participant confidentiality. All biospecimens will be collected during visits to NIH.

#### 5.1.3 Tumor tissues

Baseline research tumor biopsies are mandatory for every subject who is deemed safely able to be biopsied by Interventional Radiologist review. Biopsies at progression are optional. If a biopsy is

done for clinical reasons, samples will also be collected for research at that time, if feasible. No more than 2 biopsies per subject will be done for research during the study.

Research biopsies will be performed under local anesthesia. General anesthesia may be provided as clinically indicated.

Pretreatment tumor biopsies will be obtained by minimally invasive methods such as CT guided percutaneous biopsies. The biopsy site will be determined by a discussion between an interventional radiologist and the study PI or AI.

Attempts will be made to obtain up to five cores if safe and feasible, which will be frozen for research studies. These tumor core biopsies will be obtained percutaneously or per vagina through interventional radiology as long as considered minimal surgical risk. Two 3-millimeter punch biopsies of skin will be acceptable in lieu of 18-gauge core biopsies for participants with skin involvement. Inability to get tissue with a reasonable attempt will not preclude treatment and the participant will remain eligible for all other translational components.

The use of imaging to facilitate biopsies will be decided upon by members of the interventional radiology team. Should CT scans be needed for biopsy, a limit of 2 scans for each procedure will be observed to minimize radiation exposure to the participant.

The schedule for the biopsies will be made with Special Procedures (e.g., [name]). Members of the Biospecimen Procession Core (BPC) will be on call to receive and embed biopsies.

- One core biopsy will be sent to the LP to confirm the diagnosis and for TROP2 immunohistochemical staining (see Section 5.2.2.1)
- The remaining core biopsies from pretreatment biopsy are to be immediately embedded, frozen, and stored, barcoded, in the BPC at -80°C until use. At least one tissue core will be paraffin-embedded, barcoded, and stored in the BPC until use.

Any required consent for optional biopsies will be documented via procedure consents presented to the participants at the time of the procedure.

## 5.2 PLANNED ANALYSES

Note: Platforms and procedures may be adjusted based upon current technology and/or collaborations in place at the time of actual analyses.

### 5.2.1 *UGT1A1* Genotyping

Results from prior SG studies indicate that the frequency of some exposure related adverse events (i.e., anemia, neutropenia and febrile neutropenia) may be higher in subjects homozygous for the *UGT1A1*\*28 allele; however, the frequencies of neutrophil count decreased and other treatment-related adverse events, notably diarrhea, did not differ among the subgroups.

*UGT1A1*\*28 allele status will be evaluated as a possible marker of toxicity. Blood sample will be collected to analyze the genomic DNA and assess genotype of the most relevant drug metabolizing enzymes and transporters. DNA will be analyzed on a PharmacoScan™ (ThermoFisher) genotyping platform that tests for 4,527 genetic variations in 1,191 drug disposition genes, including CYP (phase I metabolism) genes, non-CYP (phase I metabolism) genes, phase II metabolizing genes (including UGTs), transporters, genes involved in facilitation of drug transporters, genes involved in global regulation of drug metabolizing/transporting proteins, drug binding proteins, and drug targets.

The genes encoding the drug metabolizing enzyme UGT1A1 will be evaluated. Since PharmacoScan does not test the (TA)8 repeat in rs3064744, a fragment analysis assay to test *UGT1A1* genotype was developed by the Clinical Pharmacology Program (CPP) [98]. This assay will be used by CPP to test this allele.

#### 5.2.1.1 Analysis of circulating tumor cells (CTC)

CTCs will be assessed using ferrofluidic enrichment and multiparameter flow cytometric detection. CTCs will be identified as viable, nucleated cells, that positively express one or more epithelial or tumor markers and are negative for expression of hematopoietic markers. CTCs will be further characterized for marker expression, including TROP2.

#### 5.2.1.2 $\gamma$ H2AX-staining

Peripheral blood mononuclear cells (PBMCs) will be assessed for  $\gamma$ H2AX expression using multiparameter flow cytometry along with other markers.

### 5.2.2 Tumor studies

#### 5.2.2.1 TROP2 IHC

TROP2 expression will be assessed by IHC to evaluate concordance (or discordance) between archival tumor tissues and fresh pretreatment biopsy samples. TROP2 IHC will be performed in one representative FFPE tumor section and evaluated independently by two pathologists at CCR/Laboratory of Pathology (LP).

In previous studies, membranous expression is clinically relevant in breast and gynecologic cancers for prognosis and the use of ADC [77, 79, 91, 99, 100]. Therefore, TROP2 expression will be evaluated for membranous expression. Appropriate negative and positive controls will be performed with each case. Protein expression will be quantified using H-score calculated as follows: (1  $\times$  percentage of weak staining) + (2  $\times$  percentage of moderate staining) + (3  $\times$  percentage of strong staining) within the target region, ranging from 0 to 300 [79, 91, 99]. The final immunoreactivity score will be then classified into four ordinal categories: H score 0–9, 10–99, 100–199, and 200–300 groups [79, 91, 99]. For the case where the H scores by two pathologists fall in different H-score groups, the two pathologists review the case together and get a consensus.

Please email to [name], MD PhD at [[contact]](mailto:[contact]) as soon as the participant is scheduled for biopsy.

#### 5.2.2.2 DNA damage repair pathways

mRNA levels of key molecules of DNA damage response pathways (i.e., ATM, ATR, CCNE1 or RPA1) and/or specific mutations of genes will be assessed via Next gene sequencing/ whole genome sequencing/RNAseq along with  $\gamma$ H2AX levels. This will be performed in an exploratory fashion. Results gleaned from the preliminary laboratory data in PI's lab and findings from the latest literature may modify the other endpoints of DNA damage response pathways.

### 5.2.3 Genomic studies

#### 5.2.3.1 Circulating tumor DNA (ctDNA)

ctDNA can provide a noninvasive means of monitoring both longitudinal changes in tumor burden and participants' mutational profiles. The effects of ADCs on ctDNA and associations with

response are not fully elucidated. ctDNA will be sequenced along with tumor sequencing and will be further characterized for other mutations including *TROP2* gene.

#### 5.2.3.2 Next gene sequencing, whole genome sequencing and RNAseq

Coded, linked samples will be provided to a collaborator or core lab/company for a fee-for-service for the next generation sequencing, RNAseq, or whole genome sequencing. Gene expressions of DNA repair/replication stress response and other survival pathways will be assessed using RNAseq analyses on freshly obtained tumor biopsy and correlated with clinical outcomes. Whole genome sequencing will be performed to identify *TROP2* mutations or other gene alterations and correlated with clinical outcome.

#### 5.2.3.3 TSO500

TSO500 will be performed on archival tissue samples by the laboratory of pathology to complement the findings from RNAseq and/or whole genome sequencing. This will be a hypothesis-generating and research only test. Note that participants will not be informed of these results as they are research only.

### 5.3 STORAGE, USE, AND SHARING OF SPECIMENS AND DATA (INCLUDING FOR SECONDARY RESEARCH)

#### 5.3.1 Sample Tracking and Processing

Samples will be ordered in CRIS and tracked through a Clinical Trial Data Management system. Should a CRIS screen not be available, the CRIS downtime procedures will be followed. Samples will not be sent outside NIH without appropriate approvals and/or agreements, if required.

##### 5.3.1.1 Biospecimen Processing Core (BPC)

Samples sent to the BPC will be placed immediately on wet ice and refrigerated. The date and exact time of each blood draw should be recorded on the sample tube

Please e-mail at [[contact]](mailto:[contact]) at least 24 hours before transporting samples (the Friday before is preferred).

For sample pickup, page [name].

For immediate help, call [contact] (main BPC number) or, if no answer, [contact] (main clinical pharmacology lab number).

For questions regarding sample processing, contact [[contact]](mailto:[contact]).

Upon arrival in the BPC, samples will be centrifuged and the plasma transferred into cryovials for storage at -80 C until the time of analysis.

##### 5.3.1.2 DTB Clinical Translational Unit

As soon as the participant is scheduled, please send an email notification to the DTB Clinical Translational Unit. As soon as the sample is drawn, please call the lab at [contact] to communicate that the sample is ready, where the sample is located, and a lab member will pick up the sample.

Immediately after collection, invert the blood tubes 8-10 times. Blood samples must be kept at room temperature. The blood samples will be picked up by a member of the DTB Clinical Translational Unit.

### 5.3.2 Sample Storage and Disposition

Barcoded samples are stored in barcoded boxes according to stability requirements. Access to stored clinical samples is restricted. Unless other permission obtained, samples are only to be used for research purposes associated with this trial (as per the IRB-approved protocol) by investigators named on the protocol. It is the responsibility of the Principal Investigator to ensure that samples are being used in a manner consistent with IRB approval.

Sample barcodes are linked to participant demographics and limited clinical information. This information will only be provided to investigators listed on this protocol, via registered use of a sample tracking database (e.g., Labmatrix). It is critical that the sample remains linked to participant information such as race, age, dates of diagnosis and death, and histological information about the tumor, to correlate results with sample characteristics.

### 5.3.3 Protocol Completion/Secondary Use/Sample Destruction

Any specimens remaining at the completion of the protocol will be stored indefinitely in the conditions described above. The study will remain open so long as sample or data analysis continues. All samples and data from consenting participants will be stored in identifiable format until they are no longer of scientific value or if a participant withdraws consent for their continued use, at which time they will be destroyed.

If, at any time, a participant withdraws from the study and does not wish for their existing samples to be utilized, the individual must provide a written request. Following receipt of this request, the samples will be destroyed or returned to the participant, if so requested. The participant's samples and data will be excluded from future distributions, but those which have already been distributed for approved research use will not be able to be retrieved.

The PI will record any loss or unanticipated destruction of samples as a deviation. Reporting will be per the requirements of Section [7.2](#).

through a code available to the study team, will be stored indefinitely and used for secondary research, including genetic research. Furthermore, the data and/or specimens, may be shared with other investigators in identifiable or coded (code key not available to recipient) format for secondary research. Any investigator conducting secondary research in human subjects will seek either additional regulatory approval or exemption for research as appropriate.

Data will also be shared in public database per the study's data sharing plan in compliance with NIH policies.

In addition, specimens/data may be anonymized and further research, including genetic research, conducted at the site or other institutions without participant consent. Participants will be informed that the possibility for this type of research exists.

## 5.4 SAMPLES FOR GENETIC/GENOMIC ANALYSIS

### 5.4.1 Description of the scope of genetic/genomic analysis

One of the exploratory endpoints of this protocol is to characterize mutations which predict response and changes associated with the development of chemoresistance. To this end, whole and targeted exome sequencing will be performed on tumor samples collected pre-treatment, on-treatment and/or post-progression. Genetic/genomic analysis will be performed by the core lab/company for a fee-for-service.

#### **5.4.2 Description of how privacy and confidentiality of medical information/biological specimens will be maximized.**

Initially the samples of each participant will be barcoded. At no time will participant's names be used on the blood and tissue samples. Sometimes, because a group collaboration or journal policy requires it, a subject's genetic data will be deposited in a database such as dbGaP. Although there is controlled access to such a database, such a submission carries theoretical risks of revealing the identity of the subject. This is discussed in the consent.

#### **5.4.3 Management of Results**

Whole genome/exome sequencing on this study is limited to tumor samples. No germline whole genome sequencing is performed; therefore, it is not feasible to return secondary findings. If we encounter a medically significant incidental finding, we may coordinate with the IRB, the ethics consult service, and the genetic consult service to explore on a case-by-case basis.

### **6 DATA COLLECTION AND EVALUATION**

#### **6.1 DATA COLLECTION**

The PI will be responsible for overseeing entry of data into a 21 CFR Part 11-compliant data capture system provided by the NCI CCR and ensuring data accuracy, consistency and timeliness. Principal Investigator, associate investigators/research nurses and/or a contracted data manager will assist with the data management efforts. Primary and final analyzed data will have identifiers so that research data can be attributed to an individual human subject participant.

All adverse events (AEs), including clinically significant abnormal findings on laboratory evaluations, regardless of severity, will be followed until return to baseline or stabilization of event.

Document AEs from the first study intervention, Study Day 1 through 30 days after the subject received the last product administration. Beyond 30 days after the last intervention, only adverse events which are serious and related to the study intervention need to be recorded.

An abnormal laboratory value will be recorded in the database as an AE only if the laboratory abnormality is characterized by any of the following:

- Results in discontinuation from the study
- Is associated with clinical signs or symptoms
- Requires treatment or any other therapeutic intervention
- Is associated with death or another serious adverse event, including hospitalization.
- Is judged by the Investigator to be of significant clinical impact
- If any abnormal laboratory result is considered clinically significant, the investigator will provide details about the action taken with respect to the test drug and about the participant's outcome.

The PI (or designee) evaluation of each AE not captured in the clinical database determining that it meets the criteria above will be documented in the source documents. Note: the investigator

performing the assessment must be a clinician licensed to diagnose and listed on the FDA Form 1572.

**End of study procedures:** Data will be stored according to HHS, FDA regulations, and NIH Intramural Records Retention Schedule as applicable.

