### 3.3 ON STUDY ASSESSMENTS/EVALUATIONS

#### 3.3.1 Timing of Procedures

The following describes all tests and procedures to be conducted during treatment.

Refer to Study Calendar (Section 3.4) for timing and applicable windows.

For each time period, consider the following order of assessments:

- **Screening:** Refer to Section 2.3.
- **Baseline/Cycle 1 Day 1:** The results of all assessments must be available and reviewed prior to initiation of the study drug administration to ensure results still meet standards defined in eligibility criteria. All subjects are required to complete baseline evaluations per the Study Calendar (Section 3.4) within 10 days prior to the first planned dosing of the study drugs, except for imaging tests that are required to be done within 14 (+3) days prior to treatment initiation. Any screening tests performed within the specified time frame for baseline do not need to be repeated.
- **Subsequent Cycles:**
  - Each cycle is 21 days. Beginning with Cycle 2, a permitted range of  $\pm 7$  days due to scheduling or logistical reasons is permitted; however, day 1 of SG in a new cycle may be dosed no less than 14 days from the previous dose of SG (Day 8; [i.e., the Day 8 infusion will be counted as the first day of that 14-day period]). The Day 8 dose of SG may be given no earlier than 6 days from the Day 1 dose (-1/+2 days). The scheduled Day 1 and Day 8 infusions may be delayed for up to 3 weeks for treatment-related toxicities.
  - Pre-Day 1 of each cycle assessment may be done up to 4 days (-4) prior to the start of the cycle.
  - The results of all assessments must be available and reviewed prior to initiation of study drug administration in a new cycle to confirm safety and eligibility for ongoing treatment administration. Components of these panels that are specifically relevant to monitoring the effects of the study drug are specified in “Laboratory Assessment” later in this section. The remaining laboratory values collected on these panels are part of standard of care assessments and unrelated to research. The cycle should be delayed if these criteria are not met (refer to Dose Modifications, Section 3.2.1).

- **Study Drug Administration:**
  - SG will be administered IV on D1 and D8 of 21-day cycles.

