## 5 CORRELATIVE STUDIES FOR RESEARCH

### 5.1 BIOSPECIMEN COLLECTION

#### 5.1.1 Sample Collection Table

Test/assay	Type of tube a and volume	Collection point	Location of specimen analysis b
Blood Samples			
Circulating tumor DNA (ctDNA)	2x10mL Streck Tube	C1D1(prior to treatment), C1D8 & C3D1 (within 48 hours after the SG dose), EOT/at progression	Biospecimen Processing Core (BPC)
Circulating tumor cells (CTC)	1x10 mL Streck Tube	C1D1(prior to treatment), C1D8 & C3D1 (within 48 hours after the SG dose), EOT/at progression	DTB Clinical Translational Unit
$\gamma$ H2AX expression	2x8 mL CPT blue/black tube	C1D1(prior to treatment), C1D8 & C3D1 (within 48 hours after the SG dose), EOT/at progression	
UGT1A1 genotyping	1x6 mL Lavender-top tube (K2EDTA)	C1D1 (prior to treatment)	BPC
Tumor Samples			
TROP2 IHC	FFPE , 1 core	Archival FFPE tissue if available, C1D1 (prior to treatment, mandatory except as noted in Section 5.1.3), EOT/at progression (optional) c	BPC/LP
Evaluation of DNA damage repair and other pathway genes (Next gene sequencing, whole genome sequencing and RNAseq)	FFPE/fresh frozen tissues, 3 cores		BPC/fee-for-service Core lab
TSO500	Archival, 10 unstained slides or tissue block	Archival FFPE tissues, C1D1 (prior to treatment)	LP

- a. Please note that tubes and media may be substituted based on availability with the permission of the PI or laboratory investigator.
- b. The location of specimen analysis may be adjusted at the time the analyses are performed
- c. Biopsies may be not performed on the specific dates and times due to the following reasons, including but not limited to, delayed recovery of hematologic toxicities, delayed clinic schedule, or national holidays

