## 8.2 ASSESSMENT OF SAFETY EVENTS

AE information collected will include event description, date of onset, assessment of severity and relationship to study product and alternate etiology (if not related to study product), date of resolution of the event, seriousness and outcome. The assessment of severity and relationship to the study product will be done only by those with the training and authority to make a diagnosis and listed on the Form FDA 1572 as the site principal investigator or sub-investigator.

AEs occurring during the collection and reporting period will be documented appropriately regardless of relationship. AEs will be followed through resolution.

SAEs will be:

- Assessed for severity and relationship to study product and alternate etiology (if not related to study product) by a licensed study physician listed on the Form FDA 1572 as the principal investigator or sub-investigator.
- Recorded on the appropriate SAE report form, the medical record and captured in the clinical database.
- Followed through resolution by a licensed study physician listed on the Form FDA 1572 as the principal investigator or sub-investigator.

With the exception of any listed in Section 8.4, reporting is required for all serious adverse events occurring from the first study intervention, Study Day 1, through 30 days after the subject received the last product administration. After 30 days, only adverse events which are serious and related to the study investigational agent need to be reported.

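### AE recording and sponsor SAE reporting start at Study Day 1, so complications of the mandatory pre-treatment research biopsy that begin before that day are not captured as written

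*Combined protocol and SAP*

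**What the plan says.** Two sections set the start of safety capture. Section 6.1 (Data Collection) reads: "Document AEs from the first study intervention, Study Day 1 through 30 days after the subject received the last product administration". Section 8.2 (Assessment of Safety Events) says "reporting is required for all serious adverse events occurring from the first study intervention, Study Day 1, through 30 days" after the last administration. Section 8.2 also says "AEs occurring during the collection and reporting period will be documented appropriately regardless of relationship". Within the period, then, cause does not matter; outside it, only serious and related events after day 30 are kept.

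Section 5.1.3 (Tumor tissues) says "Baseline research tumor biopsies are mandatory for every subject who is deemed safely able to be biopsied by Interventional Radiologist review", with up to five cores attempted. The sample table in 5.1.1 times this biopsy at "C1D1 (prior to treatment, mandatory except as noted in Section 5.1.3". The study calendar (3.4) places it in the Baseline/C1D1 column, and section 3.3.1 asks for baseline evaluations "within 10 days prior to the first planned dosing of the study drugs".

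Section 12.3.1.2.4 gives the risks of needle biopsy as infection, hematoma and bleeding, with puncture of lung or bowel as a rare event. It also describes the procedure as typically very safe.

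**The concern.** The biopsy is an invasive research procedure that the protocol requires. It comes before the first dose, while the stated start of capture appears to be the first dose. If so, a bleed or infection arising in between has no place in the AE database and triggers no SAE report to the sponsor under section 8.

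The loss may also be selective. Some of the listed complications could make a participant ineligible before dosing, so the more serious ones may be the likeliest to leave no safety record. What is at stake is oversight of a mandatory procedure and a complete account of its harms. The ORR result and the SG toxicity profile are not at stake.

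**Working it through.** The plan states no figure on this point, so the check is mainly of the text, followed by an illustration of scale.

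**1. When capture starts.** Sections 6.1 and 8.2 use the same phrase, joining the first study intervention to Study Day 1. No section starts AE or SAE collection at consent or at the first protocol procedure.

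**2. What the phrase means.** Study Day 1 is undefined. Several places point to the first SG dose:
- Section 2.4.1 defines screen failures as people who consent but are not assigned to the study intervention, which is SG treatment.
- Section 6.1 closes the same window at the last product administration.
- The late-event rule in 8.2 refers to the investigational agent where the matching sentence in 6.1 refers to the study intervention.
- Section 8.1.1 defines an AE in someone given a pharmaceutical product.

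**3. When the biopsy happens.** It is before treatment (5.1.1), in a calendar column whose window reaches back 10 days (3.3.1, 3.4). The uncovered interval is therefore 0 to 10 days. It is zero if the biopsy is done on Day 1.

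**4. Participants biopsied but never dosed.** Section 3.3.1 requires results to meet eligibility standards before dosing. Active infection requiring antibiotics, or recent GI perforation, hemorrhage or hemoptysis, is an exclusion (2.1.2.10, 2.1.2.12), and hemoglobin must be at least 9.0 g/dL (2.1.1.4.5). Failure to maintain eligibility before treatment takes the participant off study (3.6.2). The minimum screen-failure record is demography, failure details and eligibility criteria (2.4.1). The toxicity population in 10.4.1 requires at least one dose.

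**5. Whether other provisions close the gap.**

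| Provision | Covers | Leaves open |
|---|---|---|
| 8.2, recording regardless of relationship | Biopsy complications with onset on or after Day 1 | Earlier onset |
| 3.4, symptom/AE row ticked at Baseline/C1D1 | A contact at which an event could be noticed | 3.3.2 says symptom review sets a baseline, so an event could be logged as a baseline condition |
| 7.2.1, Policies 801 and 802 | IRB reporting, no Day 1 limit stated | AE database and sponsor SAE report |
| 7.2.3 | Deaths within 30 days of a research intervention, unless due to progression | Non-fatal events |
| 8.1.5 | Relatedness to study product | No term for relatedness to a procedure |

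**6. Scale.** Section 10.3 allows 66 evaluable participants plus 9 inevaluable, and 66 + 9 = 75. The documents give no complication rate. The rates *p* below, for complications with onset before Day 1, are assumptions. Expected events = *n* × *p*; chance of at least one = 1 − (1 − *p*)^*n*.

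| *n* | *p* | Expected | Chance of at least one |
|---|---|---|---|
| 66 | 1% | 0.66 | 48.5% |
| 66 | 2% | 1.32 | 73.6% |
| 66 | 5% | 3.30 | 96.6% |
| 75 | 1% | 0.75 | 52.9% |
| 75 | 2% | 1.50 | 78.0% |
| 75 | 5% | 3.75 | 97.9% |

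If all three cohorts stopped after stage one (3 × 10 = 30 participants), 1% to 5% gives 0.3 to 1.5 events. The 75 does not include any of the 20 allowed screen failures who were biopsied before failing; the documents do not say how many that might be.

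**The case against.** The strongest reply is that the text is ambiguous and does not plainly exclude the biopsy. Nothing states that Study Day 1 is the first SG dose. The window opens with the word intervention and closes with product administration, so the opening could be meant more broadly. The biopsy's nominal time is C1D1, so it may fall on Day 1 itself. Capture tied to dosing also suits a secondary objective that concerns the safety of SG.

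Part of this stands. A biopsy done on Day 1 is arguably covered, and the 10 days is a maximum. But the uses of the terms in 2.4.1 and 8.1.1 favour the dosing reading. If the sponsor did mean the biopsy to open the window, adding Study Day 1 conflicts with a biopsy done on an earlier day. Either way the wording needs correcting. That the objective is SG safety explains why these events should be listed separately; it does not explain leaving them unrecorded.

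A reader might infer two stronger things:
- That all biopsy complications fall outside the safety data, leaving no complication rate. The documents do not support this, because 8.2 records events with onset on or after Day 1, such as a delayed infection, whatever their cause.
- That a serious complication would go unreported to the IRB. This does not follow from 6.1 or 8.2. IRB reporting is set by 7.2 through policies whose content is not in the documents, and 7.2.3 covers certain deaths.

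**Conclusion.** The point holds in a limited form. As written, biopsy complications with onset before Study Day 1, including those in participants never dosed, fall outside the AE database and sponsor SAE reporting. The record of biopsy harms would therefore be incomplete. This rests on reading Study Day 1 as the first SG dose, which is the most natural reading but not a stated definition, and on at least some biopsies being done before that day.

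The size is small: at most about 0.7 to 3.8 events at an assumed 1% to 5% with full accrual. This should not be read as a forecast of lost events. The rate has no source in the documents. The count assumes that every participant is biopsied and, if the rate is taken as an overall complication rate, that every complication begins before Day 1. It also mixes minor and serious events. The primary ORR analysis and the sample size do not change. This is a cheap improvement worth making because a stated start rule, and not merely missing detail, leaves out harms of a required invasive procedure.

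**What to change.** 1. Define Study Day 1 as the date of the first SG dose.
2. Amend 6.1 and 8.2: AEs and SAEs related to protocol-mandated procedures are recorded, and reported to the sponsor, from the start of the research biopsy, whether or not the participant is later dosed. All other AEs are recorded from the first dose.
3. Add a related-to-study-procedure category to 8.1.5, and align 8.1.1 so that an event after a mandated procedure but before dosing counts as an AE.
4. List these events separately, with all participants biopsied as the denominator, and leave the SG toxicity population in 10.4.1 based on dosing.

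Changing only the start date in 6.1 and 8.2 would not be enough, because 8.1.1, 8.1.5 and 10.4.1 are tied to the product or to dosing. The cost is a few extra AE entries, one extra listing and small conforming edits.
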